Revised: January 7, 2021

Study Title: A placebo controlled, randomized clinical trial of galcanezumab for vestibular migraine: The INVESTMENT study

Document Date: 1/7/21

NCT: NCT04417361

Study Protocol

Title:

A Pilot Trial of Galcanezumab for Vestibular Migraine

Short Summary:

Vestibular migraine (VM) has been recognized a distinct subtype of migraine that causes dizziness as the predominant symptom. Criteria for diagnosis have been adopted by the Barany Society. Previous epidemiological research from my team has shown that it affects 2.7% of the adult population of the United States. Yet, despite its high prevalence, there is very little data upon which to guide treatment decisions. A Cochrane review in 2015 concluded that there were no placebo-controlled trials in VM, and none have been done since then. Our team recently developed and validated a patient reported outcome tool for VM, called VM-PATHI (VM-Patient Assessment Tool and Handicap Inventory). Anecdotal evidence suggests that CGRP antagonists, such as Galcanezumab, may be effective in reducing or eliminating symptoms in VM. Therefore, we propose a pilot study of changes in VM-PATHI scores, comparing active treatment (Galcanezumab) to placebo arms.

Hypothesis:

Galcanezumab will result in greater in a greater reduction of scores on the VM-PATHI (Vestibular Migraine Patient Assessment Tool and Handicap Inventory) than placebo, when comparing scores at baseline to scores after three months of treatment, between active treatment and placebo arms.

Study Objectives:

Primary:

To assess the efficacy of galcanezumab in treating vestibular migraine, as assessed by VM-PATHI (Vestibular Migraine Patient Assessment Tool and Handicap Inventory) score change between baseline (month 0) and after three months of treatment (month 4), comparing active treatment and placebo arms.

Secondary:

To assess the efficacy of galcanezumab in treating vestibular migraine, as assessed by baseline definitive dizzy days (month 0 to 1), compared to during the third month of treatment (months 3 to 4), between active treatment and placebo arms.

Definitive dizzy days will be assessed by a daily query via text message, and consist of any day where dizziness is rated as a 2 (moderate) or higher.

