To assess the response rate of subjects to galcanezumab in vestibular migraine, as measured by a 100%, 75%, 50%, and 25% reduction in definitive dizzy days, comparing baseline data (month 0 to 1), to after treatment data (months 3-4), comparing between active treatment and placebo arms.

To assess the time course of response to galcanezumab in vestibular migraine, measured by definitive dizzy days per month, comparing active treatment and placebo arms, from months 0 to 4.

To assess the efficacy of galcanezumab in treating vestibular migraine, as assessed by DHI (Dizziness Handicap Inventory) score change between baseline (month 0) and after three months of treatment (month 4), comparing active treatment and placebo arms.

To assess the efficacy of galcanezumab in treating quality of life in vestibular migraine, comparing the change in baseline PROMIS SF v1.2- Global Health scores to scores after 3 months of treatment (at month 4), across active treatment and placebo arms.

Study Endpoints:

Primary:

VM-PATHI (Vestibular Migraine Patient Assessment Tool and Handicap Inventory) score.

Secondary:

Definitive dizzy days, measured with a daily text message, with any day where dizziness is rated as a 2 (moderate) or higher counting as a definitive dizzy day.

Response rates, as measured by percentage of subjects in each arm experiencing a 100%, 75%, 50%, 25%, 0% reduction in definitive dizzy days.

Dizziness Handicap Inventory
PROMIS SF v1.2- Global Health

Statistical Methods:

Primary Endpoint:

VM-PATHI score changes between baseline and after treatment (month 4) will be compared between active treatment and placebo arms using a paired two-tailed t-test.

Secondary Endpoint:

Definitive dizzy days/month, comparing baseline to after treatment, between active treatment and control arms, will be assessed using a paired two-tailed t-test.

Response rates will be reported per category (100%, 75%, 50%, 25%, and 0%) for both active treatment and control arms. Number of subjects who experience 50% or better reduction in dizziness days will be compared using chi squared test.

Dizziness Handicap Inventory will be compared between active treatment and control arms, looking at change in score from baseline to month 4, using a paired two-tailed t-test.

PROMIS scores, comparing subdomain score changes from before (month 0) and after (month 4) treatment, across active and placebo arms, using paired t-test

Subject Selection:

Inclusion criteria:

- Adult age 18 to 75

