- Diagnosis of definite or probable vestibular migraine per Barany society criteria
- Baseline (SV1) and SV2 VM-PATHI score > 25
- Baseline (month 0 to 1) definitive dizzy days > 4
- Fluency in English
- 80% adherence or better to daily SMS during baseline phase
- Written informed consent
- Access to email, and cell phone

Exclusion criteria

- Vestibular hypofunction (unilateral or bilateral)
- History of ear surgery (other than ear tubes)
- Other vestibular diagnosis (excluding treated BPPV- Benign Paroxysmal Positional Vertigo).
- Failure of treatment with > 4 prophylactic migraine medications
- Prior or current treatment with a CGRP medication
- Pregnant/breastfeeding if female
- History of serious medical or psychiatric disease, at the discretion of the treating physician (including significant coronary artery disease, peripheral vascular disease, cerebrovascular disease, kidney disease, liver disease, and uncontrolled psychiatric disease or past psychiatric hospitalization)
- Unwilling to use approved form of birth control during the study
- Ok if on up to 2 migraine prophylactic medications (prescribed for that purpose), dose must be stable for 2 months prior to study start.

Study design: Interventional

Randomization Radio: 1:1 placebo: 120 mg galcanezumab (with 240 mg loading dose at month 1)

Comparator Description: Subjects will be compared between active treatment and placebo groups

IND: exempt

Off Label: no

Sample size: 25 per arm, or 50 total

Sample size justification: This is intended to be a pilot study, as there is currently no data available. Therefore, one main aim of this study is to better inform sample size calculations for a larger study. We have chosen 50 subjects, or 25 per arm, as a reasonable number that should help provide data to inform whether or not a larger study would be useful, assuming a 10-20% drop out rate.

Scientific Justification and background:

The objective of this study is to address whether galcanezumab is more effective than placebo at reducing dizziness in patients with vestibular migraine. Vestibular migraine is a distinct subtype of migraine that causes episodic vertigo/dizziness, sometimes with headache, and sometimes without. However, unlike traditional migraines, patients generally seek out care

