- Randomization will be done based on meeting final study criteria at SV2. So, if two patients are seen on the same day for SV1 and SV2, it would be the order of patients being seen at SV2. This would only come into play if the patients are part of the same randomization schedule (i.e. same sex and diagnosis). If however, two or more patients in the same randomization strata are seen for SV2 on the same day, given that the prescription is picked up in the AM, if the first patient does NOT meet study criteria, then we will keep the order of randomization (because the drugs are prelabelled for each patient)- but subsequent to that the next subject in that strata who is randomized should take the place of the subject who didn't meet criteria, so as to avoid disruptions to the randomization strategy.

- Packaging and labeling of test and control treatments will be identical to maintain the blind.
- Each subject will be given an identical study packet, containing their assigned drug, along with study information.
- The study blind will be broken on completion of the clinical study and after the study database has been locked. Investigators will be made aware of their subjects' treatment designations only after all the data has been collected and analyzed.
- During the study, the blind may be broken only in emergencies when knowledge of the patient's treatment group is necessary for further patient management. When possible, the Investigator should discuss the emergency with the Medical Monitor prior to unblinding. If it is determined that it is medically necessary to break the blind, the medical monitor will inform the investigator about the study status of that subject. That will be considered a protocol violation, and that subject will be removed from the study.

Intervention:

The study drug will be administered with a subcutaneous injection of galcanezumab or placebo. The first dose (at month 1) will be a loading dose of two injections, or 240 mg in total. After that, at month 2, and month 3, each subject will get either a subcutaneous injection of galcanezumab 120 mg or placebo. The injections will be with a pre-loaded syringe containing either galcanezumab or placebo.

Quality Assurance:

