- Early Discontinuation of Study Drug:**

- o A subject may be discontinued from study treatment at any time if the subject, the investigator, or the Sponsor feels that it is not in the subject’s best interest

to continue. The following is a list of possible reasons for study treatment discontinuation:

- Subject withdrawal of consent (or assent)
- Subject is not compliant with study procedures
- Adverse event that in the opinion of the investigator would be in the best interest of the subject to discontinue study treatment
- Protocol violation requiring discontinuation of study treatment
- Lost to follow-up
- Sponsor request for early termination of study
- Positive pregnancy test (females)

If a subject is withdrawn from treatment due to an adverse event, the subject will be followed and treated by the Investigator until the abnormal parameter or symptom has resolved or stabilized. All subjects who discontinue study treatment should come in for an early discontinuation visit as soon as possible and then should be encouraged to complete all remaining scheduled visits and procedures. All subjects are free to withdraw from participation at any time, for any reason, specified or unspecified, and without prejudice. Reasonable attempts will be made by the investigator to provide a reason for subject withdrawals. The reason for the subject's withdrawal from the study will be specified in the subject's source documents.

c. Analysis of Primary Endpoint:

d. For the primary endpoint, which is the change in VM-PATHI scores between month 1 and month 4 as compared between the galcanezumab arm and the placebo arm, a paired two-tailed Student's t-test will be used, provided the data is normally distributed. This will be conducted with an intent-to-treat analysis. Significance will be set at alpha of 0.05.

e. Analysis of Secondary Endpoints:

Definitive dizzy days/month, comparing baseline (month 0 to 1) to after treatment (month 3-4), between active treatment and control arms, will be assessed using a two-tailed t-test.

Response rates will be reported per category (100%, 75%, 50%, 25%, and 0% reduction in definitive dizziness days, comparing month 0 to 1 to month 3 to 4) for both active treatment and control arms. Number of subjects who experience 50% of better reduction in dizziness days will be compared using Chi Squared test.

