Dizziness Handicap Inventory will be compared between active treatment and control arms, looking at change in score from baseline to month 4, using a two-tailed t test.

PROMIS scores comparing active and placebo arm score changes from before (month 0) and after (month 4) treatment using a paired t-test.

Safety and tolerability data will be summarized by treatment group.

Adverse event rates will be coded by body system and MedDra classification term. Adverse events will be tabulated by treatment group and will include the number of patients for whom the event occurred, the rate of occurrence, and the severity and relationship to study drug.

Initially data will be summarized overall, by patient, and by treatment and control groups. Plots of each outcomes will be displayed graphically over longitudinal time points. Univariate summaries of all variables overall, by patient, and by subgroup will include means and standard deviations for continuous variables and counts and percentages for categorical variables.

Bias:

Bias will be minimized by using a double-blinded study design, with allocation concealment. This will limit selection, performance, and detection bias. In addition, this will help control for potential confounding variables. In addition, by including a placebo control group, we will minimize regression to the mean bias. Finally, by collecting information prospectively, we will minimize reporting bias.

Missing Data:

We will minimize missing data by having the clinical trial coordinator present to help the study subject fill out all data. We anticipate a 15-20% loss to follow up, and have accounted for that in our sample size calculations. Outliers and non-compliant subjects will be included in the analysis. We will perform an intent-to-treat analysis.

Trial Duration:

We estimate that this trial will take approximately 2 years to complete, once subject recruitment is able to begin. That includes 1.5 years for subject recruitment and data collection, and 6 months for closeout and data analysis. If recruitment is slower than expected, we will plan on keeping the trial open for a longer period of time. This seems unlikely based on our prior experience with recruitment in this patient population.

Pharmacy/Study Drug:

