The active drug and placebo will be managed through the research pharmacy at UCSF. The drug and placebo will be supplied by Eli Lilly and Company. Study drugs will be given to patients on the day of randomization (month 1), so any failure of subjects to take the study drugs will just be considered a violation of protocol, but they will be included in the intent to treat analysis.

Packaging:

Study drug will be supplied in preloaded syringes, each with a dose of 120 mg or placebo. Subjects will first receive the first month's supply (240 mg or placebo) at study visit 2, and then will receive a two-month supply at study visit 3. So, at study visit 2 and 3, each participant will get two pre-filled syringes. They will also get an insulated bag with a cold pack to keep the drug cool until it can be refrigerated at home.

Labeling:

Each carton (kit) of study drug will be labeled with the required FDA warning statement, the protocol number, a treatment number, the name of the sponsors, and directions for patient use and storage.

Dosage:

The study drug will be administered in fixed dose of 120 mg. The first administration, at month 1, will be a loading dose of 240 mg. Each subsequent injection (month 2 and 3) will be 120 mg dose. There will be no dose adjustment for weight, age, or any other factors

Dispensing of Study Drug:

Drugs will be administered in a packet with a 1-month supply by the site investigator at study visit 2. They will then get the second 2-month supply at study visit 3.

Administration of Study Drug:

Subjects will self-administer the drug, with a pre-filled syringe, into an acceptable area of the body. This is typically the thigh, but also includes the abdomen, buttocks, or back of the upper arm. Study personnel will monitor with first and second injection to ensure compliance and proper administration. A note will be placed into the medical record confirming the time, date, and location of the injection (part of the body). For the third injection, the CRC will reach out to the patient to confirm injection, and then record time, date, and anatomic site of the injection. Adherence to the injection will be confirmed by asking participants to send the CRC a picture of the empty syringe. This picture will be uploaded to the REDCap record.

Storage of Study Drug:

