The protocol and consent form will be reviewed and approved by the UCSF IRB prior to study initiation. Serious adverse experiences regardless of causality will be reported to the IRB in accordance with the standard operating procedures and policies of the IRB, and the Investigator will keep the IRB informed as to the progress of the study. The Investigator will obtain assurance of IRB compliance with regulations.

Data Analysis Plan:

Subjects will be divided by study status into several groups.

1. Per Protocol Analysis
 - a. Signed Consent
 - b. 4 study visits (in person or virtual) within:
 - i. SV2 (day 30) no earlier than day 23, and no later than day 44.
 - ii. SV3 (day 60/day 30 after SV2) no earlier than day 23 after SV2, and no later than day 37 after SV2.
 - iii. SV4 (day 120/day 60 after SV3) no earlier than day 50 after SV3, and no later than day 70 after SV3.
 - c. Received same drug (galcanezumab or placebo) for all doses during the trial
 - d. Completed Day 90 injection within 7 days of target date, so 23 to 37 days after SV3
 - e. 80% or better adherence to text message
 - f. Filled out all questionnaires
2. Intent to Treat
 - a. Everyone who signed consent and got at least one dose of study drug who does not meet per protocol criteria
3. SV2 failure
 - a. Signed consent but did not meet eligibility during the baseline month (less than 80% adherence to texting, or fewer than 4 definitive dizzy days or SV2 VM-PATHI less than 25)
4. SV1 failure
 - a. Signed consent but then VM-PATHI score too low on SV1
5. Screen failure
 - a. Did not meet inclusion/Exclusion so did not sign consent

Responsibilities of Study Team Members:

[name] (Principal Investigator): [name] is an Assistant Professor in the Department of Otolaryngology – Head and Neck Surgery, and the director of the Balance and Falls Center at UCSF. [name] will serve as PI for this project, and will supervise experimental design, data analysis, and summarizing the result for public disclosures to the academic community.

[name]: Co-investigator: [name] is an Assistant Professor of Neurology, and a member of the UCSF Headache Center. She will assist will all aspects of the study.

[name]: [name] is the director of the Headache Center at UCSF, and will assist in all aspects of the study.

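### The primary VM-PATHI analysis needs one test for independent arms, one baseline, one intent-to-treat set and a rule for missing month-4 scores; adjusting for the pre-dose score would cost little.

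*Combined protocol and SAP*

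**What the plan says.** **Test.** In the synopsis, Statistical Methods reads: "VM-PATHI score changes between baseline and after treatment (month 4) will be compared between active treatment and placebo arms using a paired two-tailed t-test". Analysis of Primary Endpoint repeats the paired test, on condition that the data are normal. For secondary endpoints, the synopsis pairs dizzy days, DHI and PROMIS. The later analysis section keeps the word for PROMIS and drops it for the other two. Study Design describes a randomised, placebo-controlled comparison and mentions no matching or crossover.

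**Baseline.** The primary objective is the "score change between baseline (month 0) and after three months of treatment (month 4), comparing active treatment and placebo arms". Analysis of Primary Endpoint uses "the change in VM-PATHI scores between month 1 and month 4 as compared between the galcanezumab arm and the placebo arm, a paired two-tailed" test, so its change starts at month 1. Both inclusion lists attach the word baseline to SV1: "Baseline (SV1) and SV2 VM-PATHI score > 25". Appendix 1 collects VM-PATHI at SV1 and again at SV2, where treatment starts.

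**Analysis set.** The primary analysis is to be by intent to treat. The Data Analysis Plan defines that group as "Everyone who signed consent and got at least one dose of study drug who does not meet per protocol criteria". Pharmacy/Study Drug says that "any failure of subjects to take the study drugs will just be considered a violation of protocol, but they will be included" in the intent-to-treat analysis. On emergency unblinding, the Blinding section says: "That will be considered a protocol violation, and that subject will be removed from the study".

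**Missing scores.** The Missing Data section says "We anticipate a 15-20% loss to follow up, and have accounted for that in our sample size calculations". It describes prevention and names intent to treat, but gives no method for an absent month-4 score.

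**Covariates.** Randomisation is stratified by sex and by definite or probable diagnosis. No planned analysis uses either factor or the pre-dose score as a covariate.

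**The concern.** Three statements are wrong or contradictory as written: the paired test, the two baselines and the intent-to-treat definition. One element is absent: the handling of missing month-4 scores. Together they leave open which change score is analysed, in whom, and what happens to subjects without a final score. Those choices could be made after the data are seen. A test on change drops anyone without a month-4 score, so dropout that is related to outcome and differs between arms would bias the estimate. The sample size justification and the scientific background both say that the pilot's results will inform a larger trial, so a bias would carry forward.

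The lack of covariate adjustment is a different matter. The unadjusted comparison is valid, though usually less precise, and conservative if the stratification factors are prognostic.

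**Working it through.** **Inputs.** From the Sample Size section: difference 7 points, 25 per arm, 90% power, level 0.05. The test is two-tailed. Expected loss is 15-20% (Missing Data), 10-20% (sample size justification) or 10% (Sample Size). The standard deviation (SD) is not given as a number, nor is it said whether it refers to a single score or to a change.

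**1. The plan's own figure.** Without the SD, the 90% cannot be checked forwards. Solving backwards with the noncentral t distribution (48 df), 90% power implies SD = 7.48. The standard error is 7.48 × √(2/25) = 2.12 and the noncentrality 7/2.12 = 3.31. With the same SD:

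| Analysed per arm | Power, two-sample t-test |
|---|---|
| 25 / 25 | 90.0% |
| 23 / 22 (10% loss) | 86.6% |
| 21 / 21 | 84.1% |
| 20 / 20 (20% loss) | 82.2% |

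So the claim of more than 80% power survives even 20% loss, if 7.48 is the SD of change. If it is a single-score SD, with equal SDs at both visits and correlation 0.3, the SD of change is 7.48 × √(2 × 0.7) = 8.85. Power is then 78% at 25 per arm and 68% at 20.

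**2. The word paired.** Forming 25 arbitrary pairs across arms keeps the standard error at 2.12 but reduces the df from 48 to 24. Power is 88.8% against 90.0%. The result would also depend on how the pairs were drawn, and unequal arms would leave subjects unpaired.

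**3. Baseline.** Month 0 to 4 and month 1 to 4 are different variables, both computable from Appendix 1. Each starting score precedes dosing, so either gives an unbiased comparison of arms. The documents do not allow the difference in precision to be sized.

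**4. Analysis set.** Read literally, the Data Analysis Plan's group contains only dosed subjects who fail at least one per-protocol criterion. A subject who meets all of them is out. A subject who never takes a dose is out there but in under Pharmacy/Study Drug.

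**5. Missing scores.** Call the gap the difference in mean change between lost subjects and completers within an arm. With equal loss in both arms, bias = loss share × between-arm difference in gap. It is zero if loss and gap are the same in both arms. The gaps below, in one arm only, are illustrations. The last column takes 20 per arm, SD 7.48, 20% loss and no true effect. The standard error there is 7.48 × √(2/20) = 2.37.

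| Gap (points) | Bias at 15% to 20% loss | False-positive rate |
|---|---|---|
| 2 | 0.30 to 0.40 | 5.3% |
| 3.5 | 0.53 to 0.70 | 6.0% |
| 7 | 1.05 to 1.40 | 8.9% |

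**6. Covariates.** Let k be the month-4 SD divided by the SV2 SD, and ρ the correlation of the two scores. Neither is given. The variance of ANCOVA relative to the change-score test is k²(1 − ρ²) / (1 + k² − 2kρ). For k = 1 and ρ = 0.5 this is 0.75/1 = 0.75. Because entry requires an SV2 score above 25, SV2 is truncated and k above 1 is plausible. Power below uses SD of change 7.48, N − 5 df and the factor 1 + 1/(N − 4) for estimating one slope, where N is the total analysed.

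| k | Variance ratio, ρ = 0.3 / 0.5 / 0.7 | Power at 25 per arm | Power at 20 per arm |
|---|---|---|---|
| 1.0 | 0.650 / 0.750 / 0.850 | 97.8 / 95.9 / 93.5% | 94.1 / 90.6 / 86.8% |
| 1.2 | 0.762 / 0.871 / 0.966 | 95.6 / 92.9 / 90.3% | 90.2 / 86.0 / 82.3% |
| 1.3 | 0.805 / 0.912 / 0.991 | 94.6 / 91.8 / 89.6% | 88.5 / 84.4 / 81.4% |

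The comparators are 90.0% and 82.2%. Charging for three slopes, 1 + 3/(N − 6), as if stratification gave no balance, lowers these powers by 0.5 to 2.3 percentage points. The worst cell becomes 88.2% at 25 per arm and 79.1% at 20.

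**The case against.** The Data Analysis Plan introduces its groups as a division by study status and lists screening failures alongside intent to treat. It may be a disposition list, and the surrounding sections point to a conventional analysis that keeps non-compliant subjects. That is a likely reading, but no section writes the conventional set down. The conflict over never-dosed subjects should concern few people, since staff monitor the first two injections.

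Paired is probably a slip, as the plain t-test for dizzy days and DHI in the later section suggests. The figures above agree that little power is lost.

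Allocation stays secret until the analysis is complete, which limits choices that favour the drug. It does not tell the analyst which baseline or set to use.

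On missing data, the plan asks for an early discontinuation visit, encourages remaining visits, and accepts virtual ones. These steps reduce loss, but the plan still expects 15-20%. The 8.9% needs a one-arm gap as large as the whole hypothesised effect; smaller gaps give 5.3-6.0%.

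The ANCOVA gains rest on a back-solved SD and assumed correlations, and the one-slope charge is favourable if strata are unbalanced. This stands: the gain is likely but not certain. At SD 10, t-test power would be only 68% at 25 per arm and 58% at 20. None of this affects the contradictions in the text.

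**Conclusion.** The concern holds. The paired test and the two baselines are errors on the face of the documents, and the intent-to-treat definition contradicts the sections around it. The missing rule for month-4 scores is a gap. Mislabelling the test costs about 1 point of power. The effect of the baseline and analysis-set choices cannot be sized from the documents. Bias from missing scores is 0.15-0.20 points per point of between-arm difference in gap, and that difference is unknown.

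Covariate adjustment is an improvement, not a correction. If 7.48 is the SD of change, k is 1.0-1.3 and ρ is 0.3-0.7, it changes power at 25 per arm by between about -0.4 and +8 percentage points. Under the three-slope charge the worst case is about -2. The plan should be changed, though the planned comparison, once the word paired is removed, would be valid.

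**What to change.** - Delete paired wherever arms are compared: in the synopsis and in the primary and PROMIS analyses.
- Define baseline once as the SV2 pre-dose score, and align the objectives, both inclusion lists and the analysis sections. This changes labels only; entry thresholds stay as they are. Check the DHI and PROMIS baselines against the original Appendix 1, since the extracted table is damaged.
- Make the primary analysis an ANCOVA of month-4 VM-PATHI on arm, SV2 score, sex and diagnosis, reporting the adjusted difference and 95% confidence interval. A mixed model that also uses SV3 is an option. Use the same approach for DHI and PROMIS.
- Define intent to treat as all randomised subjects in their assigned arm, correct the Data Analysis Plan, and say whether data from subjects removed after unblinding are analysed.
- State the missing-at-random assumption. Add one sensitivity analysis that makes missing month-4 scores in the galcanezumab arm worse by a fixed amount, for example 0 to 7 points.
- Reconcile the three loss rates, and state which SD was used in Sample Size.
- Report the SV2 and month-4 SDs and their correlation, which the larger trial will need.

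The cost is protocol wording and three degrees of freedom. No new data or visits are needed.
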